## **5. TREATMENT PLAN**

### **5.2 STUDY PROCEDURES**

#### **PLACEBO-CONTROLLED PERIOD**

**Screening (maximum 30 days): The screening period begins once the informed consent is signed.**

- Informed Consent
- Inclusion/ Exclusion
- Demographics
- Medical History
- Concomitant Medications/Treatments
- Physical Exam
- Electrocardiogram
- Vital Signs (blood pressure, pulse, oxygen saturation, respiratory rate and body temperature)
- Height
- Weight
- Body Mass Index (BMI) [BMI= weight (kg)/height (m^2)]
- Patient Diary
- Patient Oriented Eczema Measure (POEM)
- Hospital Anxiety and Depression Scale (HADS)
- Dermatology Life Quality Index (DLQI)
- Investigator's Global Assessment (IGA)
- Eczema Area and Severity Index (EASI)
- Global Individual Signs Score (GISS)
- SCORing Atopic Dermatitis (SCORAD)
- Body Surface Area (BSA) involvement with atopic dermatitis (must be greater than 10%)
- Urinalysis: pH, protein, glucose and blood cells (RBCs and WBCs)
- Blood Draw:

- Chemistry panel: Albumin, Alkaline Phosphatase, ALT, AST, GGT, Bicarbonate (CO2), Calcium, Chloride, Creatinine, Glucose, Potassium, Sodium, Total Bilirubin, Total Protein, Urea Nitrogen
- Hematology Panel: Complete Blood Count (CBC) with differential and platelets
- Infectious disease screening: HIV antibody, Hepatitis C antibody, Hepatitis B panel (HBsAg, anti-HBc, anti-HBs), and interferon gamma release assay (IGRA)
- Serum pregnancy test for WOCBP
- Inflammation Markers: CRP (C-Reactive Protein), ESR (Erythrocyte Sedimentation Rate)
- Randomization to study arm (once confirmed patient has passed screening requirements).

\*\*\*Patients will be monitored at the study site at visits 1, 2, 3, 17, 18 & 19 (weeks 0, 1, 2, 16, 17 & 18) for a minimum of 30-minutes after study drug administration. Vital signs and AE assessments will be done at 30 minutes (+/- 10 minutes) post-injection.\*\*\*

**Visit 1 (Baseline/Week 0/Day 0) (must occur within 30 days of signing informed consent)**

- **At least 45 minutes before injection:** Remove syringe from refrigeration and lay flat; allow to warm to room temperature. Syringe may be held in hand to warm. Do not heat.
- Pre-injection
  - Verify patient still meets all Inclusion/ Exclusion criteria
  - Height, Weight, BMI
  - Patient Diary
  - POEM, HADS, DLQI
  - EASI, GISS, SCORAD, BSA, IGA
  - Vital signs, Urine Pregnancy
  - Urinalysis
  - Blood draw for chemistry, hematology, inflammation markers, PK/ADA, PD (including IL-6), biomarker and research analysis
- Bermekimab/placebo subcutaneous injection (To deliver a loading dose to subjects in the bermekimab groups while maintaining blinding, all subjects will receive two injections)
- Post-injection
  - Adverse event monitoring
  - Concomitant medications/treatments

**Visit 2 (Week 1/Day 7 ± 3 days); Visit 3 (Week2/Day 14 ± 3 days)**

- **At least 45 minutes before injection:** Remove syringe from refrigeration and lay flat; allow to warm to room temperature. Syringe may be held in hand to warm. Do not heat.
- Pre-injection
  - Patient Diary
  - POEM, HADS, DLQI
  - IGA, EASI, GISS, SCORAD, BSA
  - Vital signs, Urine Pregnancy
  - Blood draw for PK/ADA, PD (including IL-6), biomarker and research analysis

- Bermekimab/placebo subcutaneous injection
- Post-injection
  - Adverse event monitoring
  - Concomitant medications/treatments

**Visit 4 (Week 3/Day 21 ± 3 days); Visit 6 (Week 5/Day 35 ± 3 days)**

- ***At least 45 minutes before injection:*** Remove syringe from refrigeration and lay flat; allow to warm to room temperature. Syringe may be held in hand to warm. Do not heat.
- Pre-injection
  - Patient Diary
  - Vital signs, Urine Pregnancy
  - Blood draw for PK/ADA, PD (including IL-6), biomarker and research analysis
- Bermekimab/placebo subcutaneous injection
- Post-injection
  - Adverse event monitoring
  - Concomitant medications/treatments

**Visit 5 (Week 4/Day 28 ± 3 days); Visit 13 (Week 12/Day 85 ± 3 days)**

- ***At least 45 minutes before injection:*** Remove syringe from refrigeration and lay flat; allow to warm to room temperature. Syringe may be held in hand to warm. Do not heat.
- Pre-injection
  - Patient Diary
  - POEM, HADS, DLQI
  - EASI, GISS, SCORAD, BSA, IGA
  - Vital signs, Urine Pregnancy
  - Blood draw for chemistry, hematology, inflammation markers, PK/ADA, PD (including IL-6), biomarker and research analysis
- Bermekimab/placebo subcutaneous injection
- Post-injection
  - Adverse event monitoring
  - Concomitant medications/treatments

**Visit 7 (Week 6/Day 42 ± 3 days)**

- ***At least 45 minutes before injection:*** Remove syringe from refrigeration and lay flat; allow to warm to room temperature. Syringe may be held in hand to warm. Do not heat.
- Pre-injection
  - Patient Diary
  - POEM, HADS, DLQI
  - EASI, GISS, SCORAD, BSA, IGA
  - Vital signs, Urine Pregnancy
- Bermekimab/placebo subcutaneous injection
- Post-injection
  - Adverse event monitoring

- Concomitant medications/treatments

**Visit 8 (Week 7/Day 49 ± 3 days); Visit 10 (Week 9/Day 63 ± 3 days); Visit 11 (Week 10/Day 70 ± 3 days); Visit 12 (Week 11/Day 77 ± 3 days); Visit 14 (Week 13/Day 91 ± 3 days); Visit 15 (Week 14/Day 98 ± 3 days); Visit 16 (Week 15/Day 105 ± 3 days)**

- ***At least 45 minutes before injection:*** Remove syringe from refrigeration and lay flat; allow to warm to room temperature. The syringe may be held in the hand to warm. Do not heat.
- Pre-injection
  - Patient Diary
  - Vital signs, Urine Pregnancy
- Bermekimab/placebo subcutaneous injection
- Post-injection
  - Adverse event monitoring
  - Concomitant medications/treatments

**Visit 9 (Week 8/Day 56 ± 3 days)**

- ***At least 45 minutes before injection:*** Remove syringe from refrigeration and lay flat; allow to warm to room temperature. Syringe may be held in hand to warm. Do not heat.
- Pre-injection
  - Patient Diary
  - POEM, HADS, DLQI
  - EASI, GISS, SCORAD, BSA, IGA
  - Vital signs, Urine Pregnancy
  - Urinalysis
  - Blood draw for chemistry, hematology, inflammation markers, PK/ADA, PD (including IL-6), biomarker and research analysis
- Bermekimab/placebo subcutaneous injection
- Post-injection
  - Adverse event monitoring
  - Concomitant medications/treatments

## **BLINDED ACTIVE DOSING PERIOD**

**Visit 17 (Week 16/Day 112 ± 3 days)**

- ***At least 45 minutes before injection:*** Remove syringe from refrigeration and lay flat; allow to warm to room temperature. Syringe may be held in hand to warm. Do not heat
- Pre-injection
  - Patient Diary
  - POEM, HADS, DLQI
  - EASI, GISS, SCORAD, BSA, IGA
- Physical Examination, Vital signs, Urine Pregnancy
- Urinalysis

- Blood draw for chemistry, hematology, inflammation markers, PK/ADA, PD (including IL-6), biomarker and research analysis
- Bermekimab/placebo subcutaneous injection
- Post-injection
  - Adverse event monitoring
  - Concomitant medications/treatments

**Visit 18 (Week 17/Day 119 +/-3); Visit 19 (Week 18/Day 126 +/-3); Visit 20 (Week 19/Day 133 +/-3); Visit 22 (Week 21/Day 147 +/-3); Visit 23 (Week 22) (day 154 +/-3); Visit 24 (Week 23) (day 161 +/-3); Visit 26 (Week 25/Day 175 +/-3); Visit 27 (Week 26/Day 182 +/-3); Visit 28 (Week 27/Day 189 +/-3); Visit 30 (Week 29/Day 203 +/-3); Visit 31 (Week 30/Day 210 +/-3); Visit 32 (Week 31/Day 217 +/-3):**

- ***At least 45 minutes before injection:*** Remove syringe from refrigeration and lay flat; allow to warm to room temperature. Do not heat
- Pre-injection
  - Patient Diary
  - Vital Signs, Urine Pregnancy
- Bermekimab/placebo subcutaneous injection
- Post-injection
  - Adverse event monitoring
  - Concomitant medications/treatments

**Visit 21 (Week 20/Day 140 +/-3); Visit 29 (Week 28/Day 196 +/-3):**

- ***At least 45 minutes before injection:*** Remove syringe from refrigeration and lay flat; allow to warm to room temperature. Do not heat
- Pre-injection
  - Patient Diary
  - POEM, HADS, DLQI
  - EASI, GISS, SCORAD, BSA, IGA
- Vital Signs, Urine Pregnancy
- Bermekimab/placebo subcutaneous injection
- Post-injection
  - Adverse event monitoring
  - Concomitant medications/treatments

**Visit 25 (Week 24/Day 168 ± 3 days)**

- ***At least 45 minutes before injection:*** Remove syringe from refrigeration and lay flat; allow to warm to room temperature. Do not heat
- Pre-injection
  - Patient Diary
  - POEM, HADS, DLQI
  - EASI, GISS, SCORAD, BSA, IGA

- Vital Signs, Urine Pregnancy
- Urinalysis
- Blood draw for chemistry, hematology, inflammation markers, PK/ADA, biomarkers and research analysis
- Bermekimab/placebo subcutaneous injection
- Post-injection
  - Adverse event monitoring
  - Concomitant medications/treatments

**Visit 33 (Week 32/Day 224 +/-3)**

- Patient Diary
- POEM, HADS, DLQI
- IGA, EASI, GISS, SCORAD, BSA
- Physical Exam, Vital Signs, Urine Pregnancy
- Urinalysis
- Blood draw for chemistry, hematology, inflammation markers, PK/ADA, biomarkers and research analysis
- Adverse event monitoring
- Concomitant medications/treatments

**FOLLOW-UP PERIOD**

- POEM, HADS, DLQI
- IGA, EASI, GISS, SCORAD, BSA
- Physical Exam, Vital Signs, Urine Pregnancy
- Urinalysis
- Blood draw for chemistry, hematology, inflammation markers, PK/ADA, biomarkers and research analysis
- Adverse Events
- Concomitant medications/treatments

**UNSCHEDULED VISIT (if applicable)**

- Patient Diary
- POEM, HADS, DLQI
- IGA, EASI, GISS, SCORAD, BSA
- Physical Exam, Vital Signs, Electrocardiogram, Urine/ Serum Pregnancy
- Urinalysis
- Blood draw for chemistry, hematology, inflammation markers, infectious disease panel, PK/ADA, biomarkers and research analysis
- Adverse Events
- Concomitant medications/treatments

## **EARLY TERMINATION VISIT (if applicable)**

- Patient Diary
- POEM, HADS, DLQI
- IGA, EASI, GISS, SCORAD, BSA
- Physical Exam, Vital Signs
- Urinalysis
- Blood draw for chemistry, hematology, inflammation markers, infectious disease panel, PK/ADA, biomarkers and research analysis, Serum Pregnancy
- Adverse Events
- Concomitant medications/treatments

## 5.2 STUDY CALENDARS

### 5.2.1 Placebo-controlled Period

Study Procedure	Screening	Baseline	Placebo-controlled Period															
			V2	V3	V4	V5	V6	V7	V8	V9	V10	V11	V12	V13	V14	V15	V16	V17
Visit (V)		V1	V2	V3	V4	V5	V6	V7	V8	V9	V10	V11	V12	V13	V14	V15	V16	V17
Week (W)		W0	W1	W2	W3	W4	W5	W6	W7	W8	W9	W10	W11	W12	W13	W14	W15	W16
Day (D)	-30 to -1	D0	D7	D14	D21	D28	D35	D42	D49	D56	D63	D70	D77	D84	D91	D98	D105	D112
Visit Window (d)		±3d	±3d	±3d	±3d	±3d	±3d	±3d	±3d	±3d	±3d	±3d	±3d	±3d	±3d	±3d	±3d	±3d
Screening/Baseline:																		
Informed Consent	X																	
Inclusion/Exclusion	X	X																
Medical History/ Demographics	X																	
Height, Weight, BMI	X	X																
Randomization	X																	
Treatment:																		
Administer Study Drug/ Placebo		X 	X	X	X	X	X	X	X	X	X	X	X	X	X	X	X	X 
Conmed Procedures	X	X	X	X	X	X	X	X	X	X	X	X	X	X	X	X	X	X
Efficacy:																		
Patient Daily Diary (Pain NRS, Pruritus NRS)	X	X	X	X	X	X	X	X	X	X	X	X	X	X	X	X	X	X
POEM, DLQI, HADS	X	X	X	X		X		X		X				X				X
IGA, EASI, GISS, SCORAD, BSA	X	X	X	X		X		X		X				X				X
Safety:																		
Physical Examination	X																	X
Electrocardiogram	X																	
Vital Signs	X	X	X	X	X	X	X	X	X	X	X	X	X	X	X	X	X	X
Adverse Events		X	X	X	X	X	X	X	X	X	X	X	X	X	X	X	X	X
Laboratory Testing:																		
Infectious disease panel (HIV ab, HBsAg, Hep C Ab, TB)	X																	
Hematology, Chemistry, Inflammation Markers	X	X				X					X			X				X
Urinalysis	X	X									X							X
Pregnancy Test (WOCBP only) *X designates a urine test	Serum	X	X	X	X	X	X	X	X	X	X	X	X	X	X	X	X	X
PK/PD/ADA:																		
PK/ADA,PD (including IL-6), biomarker analysis, Research Samples (serum/plasma)		X	X	X	X	X	X			X				X				X
 30 days are allowed to complete all screening procedures and randomization.																		
 Patients will be monitored at the study site at visits 1, 2, and 3 (weeks 0, 1 and 2) for a minimum of 30 minutes after study drug administration. Vital signs and AE assessments will be done at 30 minutes (+/- 10 minutes) post-injection.																		
 Patients will be randomized to treatment arm 1, 2, or placebo and will follow the corresponding treatment plan.																		
 Assessments/procedures should be conducted in the following order: patient reported outcomes, investigator assessments, safety and laboratory assignments, administration of the study drug.																		
 Concomitant medications within 30 days before screening until 7 days after the last administration of the study drug must be recorded for the purpose of drug-drug and drug-disease interaction evaluation and signal detection																		
 Loading Doses: Treatment arm 1: 800 mg loading dose of bermekimab + placebo (one 2mL SC injection containing 400 mg of bermekimab and one 2mL SC injection of placebo) at week 0; Treatment arm 2: 800 mg loading dose of bermekimab (2 x 2mL SC injections each containing 400 mg of bermekimab) at week 0; Arm 3: 4 mL loading dose of placebo (2 x 2mL SC injections of placebo) at week 0.																		
 Patients in Arm 3 will begin to receive active bermekimab therapy at visit 17 (week 16). Patients in all arms will remain blinded through end of study.																		

## 5.2.2 Blinded Active Dosing Period

Study Procedure	Blinded Active Dosing Period																
	V18	V19	V20	V21	V22	V23	V24	V25	V26	V27	V28	V29	V30	V31	V32	V33	
Visit (V)	W17	W18	W19	W20	W21	W22	W23	W24	W25	W26	W27	W28	W29	W30	W31	W32	
Week (W)	D119	D126	D133	D140	D147	D154	D161	D168	D175	D182	D189	D196	D203	D210	D217	D224	
Day (D)	Visit Window (d)																
Treatment: 	±3d																
Administer Study Drug	X	X	X	X	X	X	X	X	X	X	X	X	X	X	X	X	
Con Meds/ Treatments	X	X	X	X	X	X	X	X	X	X	X	X	X	X	X	X	X
Efficacy:																	
Patient Diary (daily)	X	X	X	X	X	X	X	X	X	X	X	X	X	X	X	X	X
IGA, EASI, GISS, SCORAD, BSA				X				X				X				X	
POEM, DLQI, HADS				X				X				X					X
Safety:																	
Physical Examination																	X
Electrocardiogram																	
Vital Signs	X	X	X	X	X	X	X	X	X	X	X	X	X	X	X	X	X
Adverse Events	X	X	X	X	X	X	X	X	X	X	X	X	X	X	X	X	X
Laboratory Testing:																	
Infectious Disease Panel																	
Hematology, Chemistry, Inflammation Markers								X									X
Urinalysis								X									X
Pregnancy Test (WOCBP only)	X	X	X	X	X	X	X	X	X	X	X	X	X	X	X	X	X
PK/PD/ADA:																	
PK/ADA, IL-6, PD, biomarker & research samples (serum/plasma)								X									X

 Patients will be monitored at the study site at visits 1, 2, 3, 17, 18 & 19 (weeks 0, 1, 2, 18, 19 & 20) for a minimum of 30 minutes after study drug administration. Vital signs and AE assessments will be done at 30 minutes (+/- 10 minutes) post-injection.

 Patients will be randomized to treatment arm 1, 2, or 3 and will follow the corresponding treatment plan.

 Assessments/procedures should be conducted in the following order: patient assessments, investigator assessments, safety and laboratory assignments, administration of the study drug.

 Concomitant medications within 30 days before screening until 7 days after the last administration of the study drug must be recorded for the purpose of drug-drug and drug-disease interaction evaluation and signal detection

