injector(s) should have no other contact with the participant during the study, should not discuss the participant's treatment with the participant, participant's caregiver, or other site personnel at any time, and will not be permitted to review the participant's medical records, questionnaires, or the electronic CRF prior to each injection. The designated injector(s) should be documented in the source documents at each visit.

Study treatment will be administered weekly in the clinic for 31 weeks with weekly office visits for 32 weeks. Patients will remain at the study site for a minimum of 30 minutes (+/- 10 minutes) after injections at weeks 0, 1, 2, 16, 17 and 18 injections for safety monitoring.

During the 32-week treatment period, patients will attend weekly clinical study visits. Clinical assessments, collection of samples for bermekimab concentrations, and safety testing will be performed at specified clinic visits. After completion of the 36-week study period, data will be locked and analyzed for safety and efficacy endpoints for all arms. In addition to the analyses that will be performed following the formal database lock at the end of the study at Week 36, an additional database lock may be performed at Week 16, and interim analyses utilizing unblinded efficacy data available as the study progresses, may also be conducted to help plan potential future development activities. An internal interim analysis committee (IAC) will be established to review the interim data and formulate recommended decisions/actions. The IAC will consist of at least a clinician and a statistician (neither of whom are involved in study conduct or compound development), one of whom will chair the committee, and may also include other members as required by the nature of the IAs. Details will be provided in a separate IAC charter, which will define the organization and roles and responsibilities of the committee, possible recommendations or requests, and the communication process following IA reviews. Results from the Week 16 database lock and/or interim analyses will not be disseminated to investigators or subjects participating in the study. In addition, results of the interim analyses will not be disseminated to individuals associated with the conduct of the study.

Patients will be monitored at a follow up visit (visit 34/week 36) for safety and clinical assessments after completing the 32 week treatment period.

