## **7. ASSESSMENT OF SAFETY**

Safety will be assessed by monitoring adverse events, vital signs, physical examinations, ECG, and clinical laboratory measurements. Data from ECG will be included in safety analysis only when all of these measures are available for each subject (baseline and last visit). Adverse events will be monitored from visit 1 (post-injection) through visit 34 (week 36). Any serious adverse events whether related to study drug or not will be followed up until resolution.

Study drug, bermekimab, will be administered under close observation in a facility equipped to handle anaphylaxis or injection site reactions. Subjects must be closely monitored at the study site at visits 1, 2 and 3 (for the first three injections) until at least 30 minutes following the administration of the antibody. Vital signs and AE assessments will be done at 30 minutes (+/- 10 minutes) post-injection.

Any grade 3 or greater injection site reaction must be reported to the sponsor within 24 hours of learning of the event.

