The mechanism behind infusion or injection site reactions is not well understood. In some cases, it may involve a reaction against the antibody products themselves, particularly where the primary sequence of the antibody has been modified *in vitro* or is derived from non-human system or, against some minor residual component from the manufacturing process (i.e. host cell proteins). Bermekimab is derived from and has undergone immunological selection in humans, thus anti-bermekimab responses are highly unlikely. To date, there has been a very low incidence of injection site or infusion reactions observed (27 patients out of 911 total; 3.0%). In order to mitigate this class-specific risk, close monitoring is required during the bermekimab infusion/ injection and for at least 30 minutes after the end of the infusion/ injection for the first 3 doses. Availability of resuscitation equipment must be ensured although this has never been used for any patient in any of our studies. Pre-medication with antihistamines, NSAIDs or corticosteroids is not required but allowed at PI's discretion.

An expanded discussion of potential risks and monitoring with bermekimab therapy is located in Section 4.6 of the Investigator's Brochure.

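### The protocol's lists for the timed 30-minute post-injection observation disagree over Weeks 16 to 18, when Arm 3 receives its first active doses

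*Protocol*

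**What the plan says.** Five places in the protocol list the visits at which patients stay on site for observation.

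- **Synopsis, Trial Design:** patients remain for a minimum of 30 minutes "after injections at weeks 0, 1, 2, 16, 17 and 18 injections for safety monitoring".
- **Section 5.2, Study Procedures (note after the screening list):** "visits 1, 2, 3, 17, 18 & 19 (weeks 0, 1, 2, 16, 17 & 18"), with vital signs and adverse events assessed at 30 minutes, plus or minus 10.
- **Calendar 5.2.1, footnote 2:** "Patients will be monitored at the study site at visits 1, 2, and 3 (weeks 0, 1 and 2"). This is the calendar that contains the Visit 17/Week 16 column.
- **Calendar 5.2.2, footnote 2:** names visits 1, 2, 3, 17, 18 and 19 and gives them as "weeks 0, 1, 2, 18, 19 & 20". This calendar begins at Visit 18.
- **Section 7, Assessment of Safety:** "Subjects must be closely monitored at the study site at visits 1, 2 and 3 (for the first three injections").

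Two further protocol passages give these lists their meaning. Section 9.7 describes close monitoring as required, as mitigation of a class-specific risk, during administration and "for at least 30 minutes after the end of the infusion/ injection for the first 3 doses". Footnote 7 of calendar 5.2.1 states: "Patients in Arm 3 will begin to receive active bermekimab therapy at visit 17 (week 16").

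On the analysis side, SAP Section 6.1 describes injection-site reactions in the 30-minute window as recorded in the eCRF at Weeks 0, 1 and 2, and plans a summary for that time frame.

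**The concern.** The purpose given in Section 9.7 attaches to the first three doses of bermekimab. In Arms 1 and 2 active drug starts at Week 0. In Arm 3 every injection before Week 16 is placebo, so a list that stops at visit 3 covers only placebo injections in that arm. Sites are blinded and cannot pick out the Arm 3 patients at Week 16, so a single list has to serve all patients.

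Two things are at stake. The first is whether the protocol's stated mitigation reaches about a third of the trial at first exposure. The second is whether post-injection vital signs and injection-site reactions are collected in the same timed way at that exposure. SAP Section 6 defines a separate placebo-to-bermekimab safety group for events from the first active dose onward, and SAP Section 6.3 takes pre- and post-injection vital signs according to the protocol's schedule, whose footnotes are among the passages that differ.

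**Working it through.** No sample size, power or error rate is involved. The check is a mapping of visits to weeks, followed by a count.

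**Inputs**
- Visit-to-week mapping (protocol Section 5.2 and both calendars): Visit 1 = Week 0, Visit 17 = Week 16, Visit 18 = Week 17, Visit 19 = Week 18, Visit 21 = Week 20. The rule is week = visit − 1.
- First active dose in Arm 3: Visit 17/Week 16, then weekly (protocol Section 3 and calendar 5.2.1, footnote 7). The first three active doses are therefore at Weeks 16, 17 and 18.
- Size of Arm 3: about 90 patients randomized 1:1:1, so 90 / 3 = about 30.

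**Step 1: the footnote to calendar 5.2.2**
- By visit number: 17 − 1 = 16, 18 − 1 = 17, 19 − 1 = 18, giving Weeks 16, 17 and 18.
- By week number: 18 + 1 = 19, 19 + 1 = 20, 20 + 1 = 21, giving Visits 19, 20 and 21.
- Beyond the first three visits, the two halves of the footnote share only Visit 19/Week 18, so they cannot both be right.

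**Step 2: coverage of Arm 3's first three active doses (Weeks 16, 17, 18)**

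| Passage | Weeks listed | Week 16 listed? | Doses covered |
|---|---|---|---|
| Synopsis, Trial Design | 0, 1, 2, 16, 17, 18 | yes | 3 of 3 |
| Section 5.2 | 0, 1, 2, 16, 17, 18 | yes | 3 of 3 |
| Calendar 5.2.2 footnote 2, by visit | 0, 1, 2, 16, 17, 18 | yes | 3 of 3 |
| Calendar 5.2.2 footnote 2, by week | 0, 1, 2, 18, 19, 20 | no | 1 of 3 |
| Calendar 5.2.1 footnote 2 | 0, 1, 2 | no | 0 of 3 |
| Section 7 | 0, 1, 2 | no | 0 of 3 |

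**Step 3: the SAP**
The 30-minute injection-site reaction summary in SAP Section 6.1 uses Weeks 0, 1 and 2. In Arm 3 those are all placebo injections, so the summary includes 0 of that arm's first three active doses. This matches the visits 1 to 3 list, not the list in the synopsis and Section 5.2.

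**The case against.** A fair defence has four parts.

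1. **The visit list in calendar 5.2.2 is right by the mapping.** Its footnote names the same visits as Section 5.2, and only the week labels in brackets differ. This stands: read by visit, it covers Week 16, and the week labels alone could be a slip.

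2. **Calendar 5.2.1 and Section 7 omit the later visits but do not exclude them.** A site that met every stated requirement would observe patients at Weeks 16 to 18, because the synopsis and Section 5.2 are also mandatory. This stands as logic. It does not remove the need to reconcile, because the omissions are in the calendar that shows the switch visit and in the safety section, and a labelling slip explains neither. The documents do not say which page a site works from, so nothing can be concluded about actual practice.

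3. **Arm 3 would still be watched.** A reader might infer that its first active doses go unmonitored, or that reactions to them would not be captured. The documents do not support that. The Visit 17, 18 and 19 procedures in Section 5.2 include post-injection adverse event monitoring. Section 7 calls for administration under close observation in a facility equipped for anaphylaxis, with no limit by visit. Section 9.3 requires all untoward events after the first injection to be recorded. What varies between passages is the specified 30-minute stay with timed vital signs and adverse event check.

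4. **Efficacy is untouched.** This also stands: the EASI at Visit 17 is assessed before the injection, so the Week 16 primary endpoint does not depend on this schedule.

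**Conclusion.** The inconsistency is real and sits in the protocol's operative text. The timed 30-minute observation covers three, one or none of Arm 3's first three active doses, depending on the passage read. It affects about 30 of 90 patients, assuming equal allocation and that placebo patients continue to Week 16; early withdrawals would lower that number. Section 9.7 puts infusion or injection site reactions at 27 of 911 patients (27/911 = 3.0%), so few events would be expected in an arm of this size. The weight of the point comes from the protocol's own stated mitigation and from uniform data collection, not from a large expected event count.

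It is more than clerical for two reasons. The visits 1 to 3 list does not deliver the Section 9.7 mitigation to Arm 3, and SAP Section 6.1 carries that same list into the analysis. The conclusion stops there: it concerns a timed assessment whose schedule is stated inconsistently. It does not show an absence of safety monitoring, and the documents do not show which schedule sites followed. It should be corrected as a matter of safety and safety data, and it has no bearing on the primary efficacy analysis.

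**What to change.** Reconcile the synopsis (Trial Design), Section 5.2, footnote 2 of calendars 5.2.1 and 5.2.2, Section 7 and Section 9.7 so that one list, with visits and weeks matched, appears in each. The sponsor's clinicians should choose the list; no monitoring rule is proposed here. Then align the eCRF collection of 30-minute vital signs and reactions, and the injection-site reaction summary in SAP Section 6.1, to that list.

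If the Week 16 switch has already taken place, the study report should state which schedule sites followed and what timed post-injection data exist for Weeks 16 to 18.

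The cost is a protocol clarification and a short SAP edit. No visits are added, because all patients already attend weekly.
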